- If the participant passes the health questionnaire, then a DEXA assessment for osteoporosis will take place. This assessment will be based upon a DEXA scan performed for this study, or DEXA scan completed within the last year.
- If a DEXA scan is performed for this study, the scan will take place in the Human Integrative Physiology Lab, led by [name]. [name] does not have a role in the current work, but his lab will be providing this service to the PI for a fee. The Human Integrative Physiology Lab is in the Garvin Innovation Building in the CRC ([name]). A member from the research team involved in this IRB application will meet the subject at this location to provide a lead. Trained staff in this lab will conduct the scan.
- If the participant passes the DEXA scan, she/he will have completed our screening process.
- A copy of the informed consent form will be delivered to the participant, and the first visit will be scheduled (at least 24 hours after delivery of the informed consent form).
- The investigator will meet the participant in our research lab. The investigator will confirm the inclusion criteria and ask if they have any questions about the informed consent form. All questions will be answered. If the participant still wants to participate, they will sign the informed consent form, and be provided a copy for them to keep.

Group Assignment and Training

- Participants will be randomly assigned to be either a non-balance training participant or a balance-training participant. Balance training participants will then be assigned to either TT, NT, or ST.
- If the participant is assigned to balance training, this training will be completed twice a week for three weeks. Each training session will be approximately 45 minutes in duration. The details of each type of training is described in detail in section 7.1.
- NT, TT, and ST will all be customized to participants' capabilities, and training difficulty will progressively increased based on participants' capabilities. For NT, difficulty will be increased by 1) adding the obstacle to training during all four phases, 2) leaning the participant farther forward during Phase 3, and asking subjects to walk faster during Phase 4. For TT, difficulty will be increased by increasing the maximum speed of the treadmill perturbations. For ST, difficulty will be increased by using heavier ankle

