Participants will then be screened using the 4-phase process described elsewhere in this application. If/when the participant passes this screening process, they will be provided the informed consent form (via email or physical mail), and a date and time for their first session will be scheduled. Participants will be provided at least 24 hours to review the informed consent form prior to their first session.

Written consent will take place either prior to their DEXA scan (if they are required to complete one because they do not have one over the last year) or at the start of the first session (if no new DEXA is required). Either way, and upon arrival to meeting location, the participant will be given a paper copy of the informed consent to look over and will be asked if they have any questions about the form prior to signing. As much time as necessary will be dedicated to the consent process. We will make sure participants understand their participation is entirely voluntary. We will ensure participants understand throughout the consent process by recruiting English-speaking adults, asking them if they have any questions, and if they understand the consent form.

[name] will be obtaining consent from participants.

Because our procedures involve several visits to the lab for some participations, we will ask subjects weekly how they are doing with the study and procedures, and answer any questions they might have. If necessary, we will remind them that their participation is entirely voluntary.

Non-English Speaking Subjects

- *Indicate what language(s) other than English are understood by prospective subjects or representatives.*
- *If non-English speakers will be recruited, describe the process you will use to ensure that the oral and/or written consent information provided will be in a language that they understand.*

- *If you translate consent forms and study materials, please provide a certified translation of the form as well as the certification document.*
- *Indicate the spoken language that study personnel obtaining consent will use. Describe how you will assess fluency of personnel obtaining consent to ensure that the translation is accurate.*

Non-English speaking participants will not be recruited

Waiver or Alteration of Consent Process (consent will not be obtained, required information will not be disclosed, or the research involves deception)

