25.0 Process to Document Consent in Writing

25.1 Consult “SOP: Written Documentation of Consent (HRP-091)” for recommended procedures, and describe whether and how consent of the subject will be documented in writing:

We will require written consent from each participant prior to testing.

25.2 If the research presents no more than minimal risk of harm to subjects and involves no procedures for which written documentation of consent is normally required outside of the research context, you can request that the IRB waive the requirement to obtain written documentation of consent (e.g., consent to participate is indicated by pressing a button for an online questionnaire – after the consent information is presented and before the questionnaire begins):

Considering that a verbal consent process will be used for the phone screening, we would like to request a waiver of written documentation of the consent process. For this waiver, we are expected to explain how the two criteria below have been met.

1. The research presents no more than minimal risk of harm to subjects.

The screening process that will be completed before obtaining written documentation (a questionnaire completed over the phone) presents no more than minimal risk of harm to subjects. If we need to complete a DEXA scan on any subjects, we will obtain written consent from these subjects prior to this scan.

2. The research involves no procedures for which written consent is normally required outside of the research context.

The research procedures we plan to complete prior to written consent (a questionnaire completed over the phone) do not normally require written consent outside of the research context.

25.3 If you will document consent in writing, attach a consent document with places for signatures. If you will obtain consent, but not document consent in writing, please attach the consent script or text. Review “CHECKLIST:

Waiver of Written Documentation of Consent (HRP-411)" to ensure that you have provided sufficient information. You should use "TEMPLATE CONSENT DOCUMENT (HRP-502)" to create the consent document or script:

See attached.

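### Sections 8.2, 24.1 and 25.2 conflict on whether written consent comes before or after a new study DEXA scan

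*Combined protocol and SAP*

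**What the plan says.** Three sections bear on the order of events.

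- **Section 8.2 (Recruitment and Informed Consent).** After the telephone screen and the review of the health questionnaire, "If the participant passes the health questionnaire, then a DEXA assessment for osteoporosis will take place". On its source: "This assessment will be based upon a DEXA scan performed for this study, or DEXA scan completed within the last year". Then "If the participant passes the DEXA scan, she/he will have completed our screening process". The next step is "A copy of the informed consent form will be delivered to the participant, and the first visit will be scheduled", with the visit at least 24 hours after delivery. At that visit, in the research lab, "If the participant still wants to participate, they will sign the informed consent form, and be provided a copy for them to keep".
- **Section 24.1 (Consent Process).** Verbal consent is obtained by telephone at first contact. After the four-phase screening is mentioned, the text reads "If/when the participant passes this screening process, they will be provided the informed consent form (via email or physical mail". The following paragraph then says "Written consent will take place either prior to their DEXA scan" where a new scan is required, and otherwise at the start of the first session.
- **Section 25.2 (waiver of written documentation).** "If we need to complete a DEXA scan on any subjects, we will obtain written consent from these subjects prior to this scan". The procedures that precede written consent are described there as a telephone questionnaire only.

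Section 12.1 defines the four phases. Phase 4 is the osteoporosis screening by DEXA.

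**The concern.** Section 8.2 is the only step-by-step account of recruitment, and it puts both delivery and signature of the consent form after the DEXA assessment. It provides explicitly for a scan done for the study, yet has no step that brings consent forward in that case. A team working from 8.2 would scan first and obtain the signature later.

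The stake is consent and compliance rather than inference. Section 17.1 lists DEXA radiation as a study risk. Under the 8.2 order, a research scan would rest on verbal telephone consent alone. Because the form goes only to those who pass, anyone scanned and then excluded for osteoporosis would never sign. The account given to the ethics board in 25.2 of what happens before written consent would also be untrue.

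**Working it through.** No arithmetic applies. The check sets the stated orders side by side for the two kinds of participant.

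**Participant who needs a new study scan**

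| Source | Order |
|---|---|
| 8.2 | questionnaire review → DEXA → screening complete → form delivered → at least 24 hours → form signed in the research lab |
| 24.1, form-delivery sentence | Phases 1 to 4 passed (Phase 4 is DEXA) → form sent |
| 24.1, next paragraph | paper form on arrival → signed → DEXA |
| 25.2 | signed → DEXA |

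1. In 8.2 the signature comes after DEXA. In the second paragraph of 24.1 and in 25.2 it comes before. Both cannot be followed for the same person.
2. Within 24.1, the emailed or mailed form is tied to passing a screening that includes DEXA, while the next paragraph has the form signed before DEXA. Someone who needs a scan would not yet have been sent the form when due to sign it, and would see only the paper copy handed over on arrival.
3. The 24-hour review period in 8.2 and 24.1 is counted to the first visit or first session. Neither section says whether it applies to someone who signs before a scan.
4. The scan takes place in a separate laboratory, whereas 8.2 places signature in the study's own research lab. So 8.2 cannot be read as describing a signature on arrival for the scan.
5. Section 25.1 requires written consent before testing. It does not say whether a screening scan counts as testing, so it does not settle the order.

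**Participant with a scan from the last year**

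There is no study radiation, and every source allows signature at the first session. There is no conflict for this group.

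**Who is affected**

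The conflict covers everyone who reaches Phase 4 without a scan in the last year, whether or not they pass. The documents give neither that share nor an expected number screened (14.3 is answered as not applicable), so no count can be derived.

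**The case against.** The best reply is that the two sections devoted to consent deal with exactly this case, and that 8.2 is a summary that omits a branch. It does not forbid earlier signature, and nothing gives it precedence over section 24. Section 17.2 also commits the team to telling participants about the radiation before scanning. This stands to the extent that the sponsor's intention is clear: written consent before a study scan. It does not remove the conflict, because 8.2 and one sentence of 24.1 still state the other order, and telling someone about radiation is not written consent.

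A reader might infer more than the documents support.

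- *That the waiver in 25.2 loses its minimal-risk ground.* It does not. The waiver is requested for the telephone screening, and its minimal-risk argument concerns the questionnaire. A scan before signature would fall outside the waiver and breach the commitment in 25.2, but it would not make the questionnaire riskier.
- *That 24.1 leaves people who need a scan with no form to sign.* It does not. It says that in both cases a paper copy is handed over on arrival, before signature. What conflicts is the timing of the emailed or mailed copy, and what is unclear is the review period.
- *That no consent of any kind precedes the scan.* Verbal consent is taken by telephone and documented. The gap is in written consent.
- *That all 60 participants are exposed.* This would require that nobody has a recent scan and that staff disregard 24.1 and 25.2. It is a ceiling on the enrolled participants, not an estimate, and it leaves out those who fail the scan.

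**Conclusion.** The conflict is real and lies in current text. For anyone who needs a new study scan, 8.2 and the form-delivery sentence of 24.1 place the consent form after DEXA, while the next paragraph of 24.1 and 25.2 require signature before it. The passages must be reconciled.

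The consequences depend on one assumption: that staff follow the 8.2 order. The documents do not say that they will. If they do, people without a recent scan would have a research scan without written consent, and those who fail it would never sign. The physical exposure is small on the protocol's own description (under 2 days of natural background radiation), so the harm is mainly to consent and compliance. Sample size, endpoints and analysis are unaffected.

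**What to change.** Bring the text into line with the sponsor's own commitment in 24.1 and 25.2:

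1. In 8.2, split the sequence after Phase 3. For those who need a study scan: form provided, form signed, then DEXA. For those with a scan from the last year: result reviewed, form provided, form signed at the first session.
2. In 24.1, amend the sentence that ties provision of the form to passing the whole screening, so that people who need a study scan receive it after Phase 3.
3. State whether the 24-hour review period, now tied to the first session, also applies before a study scan. Neither 24.1 nor 25.2 settles this, so the sponsor has to decide it.

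The cost is a change of protocol wording, and forms sent to some people who later fail DEXA. No visit is added: 8.2 already has a team member meet the participant at the scan site, and 24.1 already has the form reviewed and signed on arrival.

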1.0 Study Summary

Study Title	Validation and application of wearable sensors for capturing responses to losses of balance
Study Design	A three-group posttest-only design.
Primary Objective	To validate the use of wearable sensors for capturing responses to losses of balance (LOBs). During laboratory testing, we will use both wearable sensors and a laboratory-based optoelectronic motion capture system to measure responses to LOBs after laboratory-induced trips and slips. During real-world testing, we will use wearable sensors to measure responses to LOBs after any naturally-occurring trips or slips during the real-world daily lives of participants. Participants for this primary objective are referred to as "non-balance training participants."
Secondary Objective(s)	Responses to LOB measured during both laboratory testing and real-world testing will be used to compare between three types of balance training. Participants for this secondary objective are referred to as "balance training participants."
Study Population	Adults age 65-80
Sample Size	60 total including 30 non-balance training participants and 30 balance training participants.
Research Intervention(s)/Investigational Agent(s)	Data will be obtained using 1) a laboratory-based optoelectronic motion capture system to measure responses to LOBs (i.e. body movements) after laboratory-induced trips and slips, 2) wearable sensors to measure responses to LOBs after laboratory-induced and any naturally-occurring real-world trips and slips, 3) a wearable voice recorder to describe any real-world trips or slips. For balance training participants, each participants will complete one of three different research interventions: non-treadmill training (NT); treadmill training (TT); or strength training (ST). All interventions will be performed two times per week for three weeks. In this document, balance training participants will be referred to as NT participants, TT participants, or ST participants (depending upon which intervention they complete).
Study Duration for Individual Participants	The study duration for individual participants will be 5-7 weeks, not including screening.
Acronyms and Definitions	LOB - Loss of balance PBT - perturbation balance training NT - Non-treadmill training TT - Treadmill training ST - Strength and balance training

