5.0 Study Design and Statistical Analysis Plan

5.1 *Describe the basic study design/approach (e.g., qualitative study using five focus groups of first year students to describe assimilation into the university community; randomized controlled trial of a behavioral change intervention to increase dietary intake of whole grains; pre- post-test evaluation of new pedagogical techniques to improve adult literacy):*

For our primary objective, a one-group repeated-measures design will be used to validate the use of wearable sensors to capture responses to LOBs. Subjects will use wearable sensors for three weeks to capture responses to naturally-occurring trips and slips during daily life. Subjects will then complete a laboratory session to capture lab-induced LOB responses simultaneously from the wearable sensors and a gold-standard optoelectronic motion capture system.

For our secondary objective, a three-group posttest-only design will be used to compare the effects of three balance training exercises on responses to LOBs after laboratory-induced trips and slips, and two weeks of naturally-occurring real-world trips and slips. Subjects will first complete three weeks of their assigned training. Subjects will then

21-1072 Validation and application of wearable sensors for capturing responses to losses of balance

complete a laboratory session to capture lab-induced LOB responses simultaneously from the wearable sensors and a gold-standard optoelectronic motion capture system. Subjects will then use wearable sensors for two weeks to capture responses to naturally-occurring trips and slips during daily life.

5.2 Describe corresponding data analysis plan/approach (e.g., content analysis of focus group transcripts; descriptive analysis followed by linear regression modeling; nonparametric analysis of pre- and post-test measures):

Hypothesis 1: LOB response measures obtained from the wearable sensors after lab-induced trips and slips will exhibit statistical agreement with the same measures simultaneously obtained from a gold-standard laboratory-based motion capture system.

To address Hypothesis 1, a Bland-Altman analysis will be used to evaluate level of agreement between the two systems. This approach will reveal any measurement bias between the two systems, and provide bounds for these differences.

Hypothesis 2: Real-world LOB responses will show greater variety than laboratory-induced LOB responses.

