To address our secondary objective, balance training participants will be assigned to one of three balance training exercises/interventions including TT, NT, and ST. No drugs are used in this study. Each training session for TT, NT, and ST will be one-on-one with the investigator, approximately 30-45 minutes in duration, and two sessions will be completed each week for three weeks. A description of each session of each type of training follows.

Each TT session will involve a trip training protocol with a specialized treadmill (Aviles et al., 2019). TT perturbations will be induced while participants are standing on a modified treadmill (Freemotion 800, Freemotion Fitness, Logan, UT). The treadmill belt will then be accelerated posteriorly, varying in speed from 0.5 to 2.4 mph, to induce a forward LOB within about 40 msec. Participants will be instructed to react naturally and try to establish a stable gait after perturbations and an initial step over an obstacle. The treadmill belt speed will be maintained until one of two conditions are met: (1) participant established a stable gait for several strides, or (2) participant received substantial support from a fall protection harness or spotter(s) standing next to him/her. Based upon the performance of participants, the treadmill speed will progressively be increased during each session to continue challenge participants and to maintain variability over the course of training. Perturbations in the reverse belt direction (i.e., 0.5 mph anteriorly) will also be included intermittently to reduce anticipation. A slender, lightweight rectangular foam block (7.5 cm x 7.5 cm cross section) will be placed within 3-7 cm in front of the toes before each trial to elicit a step over an obstacle, similar to that needed during an actual trip. Given the suddenness of these perturbations, participants will wear a fall protection harness supported by an overhead gantry to protect knee or hand from contact with the treadmill in the event of an unsuccessful attempt to recover balance. Each TT session will involve exposure to up to 40 treadmill perturbations with a rest break after every 10 perturbations.

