8.0 Procedures Involved

8.1 Describe and explain the study design:

For our primary objective, a one-group repeated-measures design will be used to validate the use of wearable sensors to capture responses to LOBs. Non-balance training participants will use wearable sensors for three weeks to capture responses to naturally-occurring trips and slips during daily life. Subjects will then complete a laboratory session to capture lab-induced LOB responses simultaneously from the wearable sensors and a gold-standard optoelectronic motion capture system.

For our secondary objective, a three-group posttest-only design will be used to compare the effects of three balance training exercises on responses to LOBs after laboratory-induced trips and slips, and two weeks of naturally-occurring real-world trips and slips. Balance training participants will first complete three weeks of their assigned training. Subjects will then complete a laboratory session to capture lab-induced LOB responses simultaneously from the wearable sensors and a gold-standard optoelectronic motion capture system. Subjects will then use wearable sensors for two weeks to capture responses to naturally-occurring trips and slips during daily life.

8.2 Provide a description of:

- *All research procedures being performed*
- *If the study has more than one procedure, session, and/or subject population, describe each procedure, session, and/or study*

population separately. For complex studies, you are encouraged to include a figure or chart.

Recruitment and Informed Consent

- Interested participants will respond to our recruitment strategies and contact the investigators.
- The investigators will telephone interested participants and follow the telephone script included in the application to first screen participants for inclusion criteria. If participants satisfy the inclusion criteria, the investigator will continue the telephone conversation and administer the health questionnaire described in an attachment to this application. De-identified information from this health questionnaire will then be reviewed by a health professional with specialist training for the geriatric population. This specialist will be a board certified physician or board certified specialist in geriatric physical therapy.

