14.3 If applicable, indicate the number of potential subjects you expect to screen for enrollment, and the number of subjects you will need to complete the research procedures:

N/A

14.4 If the study has more than one procedure, indicate the total number of subjects to undergo each procedure separately:

30 participants will be assigned to be non-balance training participants

30 participants will be assigned to be balance training participants, with 10 completing each of the three types of training under investigation (TT, NT, ST).

Other than these differences in balance training, all other testing will be the same for all participants.

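### Does the plan leave the split into treadmill, non-treadmill and strength training open to non-random assignment?

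*Combined protocol and SAP*

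**What the plan says.** Assignment is described most fully in section 8.2, under Group Assignment and Training. The first sentence reads "Participants will be randomly assigned to be either a non-balance training participant or a balance-training participant"; the next reads "Balance training participants will then be assigned to either TT, NT, or ST". Both follow the end of screening and the consent visit, where "If the participant still wants to participate, they will sign the informed consent form".

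The other sections add no method. Section 7.1 says "balance training participants will be assigned to one of three balance training exercises/interventions including TT, NT, and ST". Section 8.1 says "Balance training participants will first complete three weeks of their assigned training". Section 14.4 fixes the numbers, "with 10 completing each of the three types of training under investigation (TT, NT, ST"). The design label in section 1.0 is "A three-group posttest-only design", and section 5.1 repeats it: "a three-group posttest-only design will be used to compare the effects of three balance training exercises". None of these calls the three-way split randomised. The supplied text describes no sequence, block size or concealment for either step.

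Section 5.2 tests Hypothesis 3 with a one-way ANOVA across NT, TT and ST, followed by Dunnett's test against ST, with unnamed covariates allowed. It tests Hypothesis 4 with an equivalence test of NT against TT.

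**The concern.** The adverb *randomly* is attached to the step that carries no formal test and is absent from the step that carries two. The trained-versus-untrained split feeds no planned hypothesis test. Hypothesis 5 names no comparator, and section 5.2 makes the real-world comparison of the trainings qualitative.

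The design makes this look more serious. A comparison made only after training is sound when chance forms the groups, because chance then stands in for a baseline measure. Balance-loss responses are measured only after training, so a starting difference in that outcome could not be seen directly. If the investigator picked the training, or could foresee the next assignment, fitter people might collect in one group. Groups of 10 give little protection. Hypothesis 3 could then be supported or missed for the wrong reason, and Hypothesis 4 could show an equivalence that is not there.

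**Working it through.** **1. The plan's own figure.** Section 14.1 gives a difference of 17.4 degrees, an SD of 12 degrees, one-sided alpha of 5%, 80% power and an independent t-test.

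- d = 17.4 / 12 = 1.45.
- Noncentrality = d × √(n/2). For n = 7 this is 1.45 × √3.5 = 2.71, with critical t (12 df) 1.782.
- Power is 0.755 at n = 6, 0.819 at n = 7 and 0.930 at n = 10.

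The stated seven per group is reproduced. How participants are allocated does not enter this calculation.

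**2. What would be at stake if assignment were discretionary.** The documents give no imbalance, no carry-over and no equivalence margin, so all three are assumed. Take a starting imbalance of 0.25, 0.5 or 0.75 SD (3, 6 or 9 degrees at SD 12), 10 per group and no covariates. Shift in the outcome δ = imbalance × carry-over.

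*No training effect, ST starts worse.* With group means (0, 0, δ) in SD units, the ANOVA noncentrality is 10 × [2(δ/3)² + (2δ/3)²] = 10 × (2/3)δ². For δ = 0.5 this is 1.67. The critical F (2, 27 df) is 3.354.

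| Carry-over | ANOVA rejects at 0.25 / 0.5 / 0.75 SD | And at least one of NT, TT favourable | And both favourable |
|---|---|---|---|
| No imbalance | 5.0% | 1.9% | 0.2% |
| 1.0 | 7.9 / 17.8 / 35.5% | 6.4 / 16.8 / 34.9% | 1.3 / 4.9 / 14.3% |
| 0.7 | 6.4 / 10.9 / 19.2% | 4.5 / 9.7 / 18.3% | 0.8 / 2.2 / 5.6% |
| 0.5 | 5.7 / 7.9 / 11.9% | 3.6 / 6.4 / 10.7% | 0.6 / 1.3 / 2.6% |

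The last two columns are simulated, with Dunnett's test taken as two-sided (critical value 2.33) because section 5.2 gives no sidedness.

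*True effect of 1.45 SD in NT and TT, ST starts better, full carry-over.* The chance of showing at least one of them better than ST falls from 89.5% to 74.6%, 53.1% and 30.7%.

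*Hypothesis 4, assumed margin 1.45 SD, true NT–TT difference equal to the margin but partly masked, full carry-over.* Two one-sided 5% t-tests (18 df) wrongly declare equivalence in 13.4%, 28.5% and 48.6% of trials, against 5.0% with no imbalance.

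These figures show how sensitive the comparison is to discretionary assignment. They say nothing about whether such assignment is planned.

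**3. What the text supports.** Reading the sections together:

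- The two sentences in section 8.2 are consecutive, under one heading. *Then* makes the second a continuation of the first.
- Section 12.1 applies one set of eligibility criteria to everyone. No section asks which training a person prefers, or directs anyone to a training by ability.
- Matching to capability happens inside each training as its difficulty rises (section 8.2), so it comes after assignment.
- Every session is one-on-one (section 7.1), and all three trainings share the same two laboratory locations (section 6.1). The text gives no class timetable or separate site that would steer people to one group.
- Section 3.2 cites the group's own earlier slip and trip training study, whose title calls it a randomised controlled trial. Section 19.1 says the team will draw on its experience with similar studies.
- Equal groups of 10 (section 14.4) are what a 1:1:1 list would deliver, though they do not prove that one exists.

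**The case for a change.** The strongest case for a change is that the protocol is what binds the team. Its text does not require chance at the step that Hypotheses 3 and 4 rely on. Every other mention of that step also omits randomness. Even if *randomly* carries forward, the supplied text describes no sequence or concealment for either step. Assigning after consent does not hide the next assignment from the person enrolling. A poor allocation cannot be undone once training has begun, and wording to prevent it would cost very little.

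Much of this stands. The method is not explicit, concealment is not described, and no later analysis can fully replace random allocation when the outcome has no baseline.

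Three things limit its weight. First, harm needs a further step that the documents do not suggest: staff allocating selectively, in a direction related to balance ability. Second, it goes too far to say that analysis could do nothing. Section 8.4 collects demographic and anthropometric data, screening (section 12.1) includes a health questionnaire and a cognitive score, and section 5.2 allows covariates for Hypothesis 3. These could reveal and partly adjust for differences in age or body size, for example. Third, the consent form was not among the pages available, so whether it describes assignment to the trainings could not be checked.

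**Conclusion.** The concern identifies missing detail and does not establish an error. On its natural reading section 8.2 describes one random process in two stages. What is unwritten, namely how the list is made and kept hidden, is something an experienced trial team would normally settle when it sets up its allocation. No stated rule gives a wrong answer, and spelling out the method would leave the sample size, group sizes, visits and tests as they are.

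The possible size is conditional. If assignment were discretionary and gave ST a 0.5 SD disadvantage, ANOVA rejection under no effect would be between 7.9% (half carry-over) and 17.8% (full carry-over), against 5%. The chance of wrongly finding both NT and TT better than ST would be 1.3% to 4.9%, against 0.2%. All of this rests on an assumed imbalance, its direction and its carry-over.

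The conclusion rests on reading the second sentence of section 8.2 as continuing the first. Evidence that training was allocated by choice or convenience would reopen the point for Hypotheses 3 and 4. The sensor-validation objective would not be affected in either case.
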